Additional Inclusion Criteria for Advanced Brain Imaging:

- No contraindications to magnetic resonance imaging (MRI) and computed tomography (CT) perfusion (CTP) study
- Stroke in the middle cerebral artery territory with a minimum diffusion-weighted imaging (DWI) lesion diameter of 20 mm on admission

Study product, dose and method of administration:

Both groups would receive a standard dose of 0.9 mg/kg recombinant tissue plasminogen activator (rtPA; alteplase) administered by IV infusion within 4.5 h after symptom onset. In addition, measures of standard care for stroke patients would be applied for both groups. Patients in the Cerebrolysin group would additionally receive 30 mL of Cerebrolysin diluted in 100 mL of normal saline administered intravenously through a separate IV line over 20 min. No treatment with other neuroprotective agents would be allowed.

Length of the Study:

Cerebrolysin treatment would be initiated simultaneously with IVT and continued once daily for 14 consecutive days. A follow-up period would be 90 days for each patient. The visits would be scheduled as follows: screening (on admission), in 24 h (visit 1), on day 7, 14, and 90 (visit 2, 3, and 4, respectively).

Endpoint evaluation:

Primary endpoint evaluation:

The study primary endpoints would be any and symptomatic HT verified on a follow-up CT scan. Symptomatic HT would be defined according to the ECASS III trial: any apparently extravascular blood in the brain or within the cranium that is associated with clinical deterioration, as defined by an increase of 4 points or more in the score on the NIHSS, or that lead to death and that is identified as the predominant cause of the neurologic deterioration.

Secondary endpoint evaluation:

Secondary endpoints would be the functional outcome measured with the National Institutes of Health Stroke Scale (NIHSS) and modified Rankin scale (mRS) as well as drug safety.

Favorable functional outcome would be defined as the mRS score of ≤ 2 at V4 (day 90).

The NIHSS score at V3 (day 14) would be considered as a marker of short-term neurological recovery.

Patients in both arms would be monitored for any adverse events (AE) at V1-3, including changes in vital signs, general and neurological condition, electrocardiogram, and routine laboratory tests (liver and kidney function tests, complete blood count).

Additional evaluation (advanced brain imaging):

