At V1 and V3, a routine brain MRI on a 1.5T scanner would be acquired followed by an axial DTI scan. The DTI sequence parameters are as follows: spin-echo echo-planar imaging, repetition time = 6000 ms, echo time = 102.9 ms, field of view = 260 mm, b-value = 0 and 1000 s/mm2, matrix = 256×256 ; slice thickness = 4.5 mm, interslice gap = 1 mm, total number of slices = 24, diffusion directions = 25, scan time = $5 \min 10$ s.

The maps of fractional anisotropy (FA), axial (AD), radial (RD) and mean (MD) diffusivity would be derived from the raw DTI scans.

At V3, a brain CT perfusion (CTP) scan would be obtained using the Dankbaar's approach. It involves a cine mode CT acquisition, with a temporal sampling rate of one image every 2 s for the first 60 s. Additional gantry rotations would be performed at 90, 120, 150, 180, 210 and 240 s. Acquisition parameters are 80 kVp and 100 mA. A bolus of 40 mL iohexol (Omnipaque, GE Healthcare, USA; 300 mg/mL of iodine) would be injected into an antecubital vein at an injection rate of 5 mL/s. CT scanning would be initiated 5 s after start of the injection of the contrast bolus. A series of CT scans covered the whole brain would be obtained with 5 mm slice thickness.

The CTP data would be processed to obtain a series of the permeability surface-area product (PS) maps.

The most representative slice would be chosen for analysis in each set of images. On that slice, the infarcted area is outlined and mirrored to the contralateral hemisphere. The values of FA, AD, RD, MD, and PS would be assessed within each region of interest.

To cope with the heterogeneity of the ischemic lesions due to different locations, absolute values of the laterality index for each parameter would be calculated using the formula:

|Laterality index| = (Affected side - Unaffected side) / (Affected side + Unaffected side) × 100%.

The infarct volume was calculated on DWI (at V1) and CT (at V3) scans according to the ABC/2 method [10].

Statistical methods

This statistical plan describes biostatistical analysis scheduled at the time of development of this study design. Detailed statistical analysis plan will be developed after study completion. Analysis report with final statistical analysis plan will be integral part of the clinical trial report.

Statistical analysis would be performed using statistical software like STATA, IBM SPSS Statistics.

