3. CLINICAL STUDY DESIGN

The study is designed to investigate efficacy of cerebrolysin 30 mL for patients with ischemic stroke during IV TLT and standard baseline therapy and early neurorehabilitation.

Therefore, the study design provides for two study groups:

Study group 1 (Cerebrolysin): 30 mL of cerebrolysin in 100.0 mL of 0.9 % NaCl during IVT, baseline therapy, early neurorehabilitation according to standards

Study group 2 (Control): IVT, baseline therapy, early neurorehabilitation according to standards

The clinical study will be carried out in patients with ischemic stroke meeting IVT inclusion and exclusion criteria (Clinical Guideline for Thrombolytic Therapy During Ischemic Stroke (National Clinical Guidelines:

http://193.232.7.120/feml/clinical_ref/0001410674S/HTML/)

The diagnosis of ischemic stroke and its localisation will be determined clinically based on neuroimaging findings (TOAST criteria).

The clinical study stipulates for follow-up period of 90 days, with 4 scheduled visits for clinical assessment at the following time points: screening (at admission), in 24 hours, on day 7, 14, and day 90.

The clinical study is expected to begin in April 2018 (first patient enrollment) and to end (final study report) by September 2020.

The clinical study is expected to be performed from 2018 till 2020.

Patient visits	Screening	Visit 1	Visit 2	Visit 3	Visit 4
Time since treatment initiation	Admission	24 hours after initiation of therapy	Day 7 after treatment initiation	Day 14 after treatment initiation	Day 90 after treatment initiation
Baseline patient information (demographic data, medical history)	+				
Inclusion/exclusion criteria review	+				
Randomisation, number assignment	+				
Non-contrast CT of the brain	+	+	+	+	
CTP* (PS)				+	
MRI* of the brain (DWI, FLAIR, 3D TOF)	+				
MRI* of the brain (DWI, DTI, 3D TOF, ROI)		+			
MRI* of the brain (DTI)				+	
Assessment of neurological impairment using to the NIHSS scale	+	+	+	+	
Assessment of disabilities using the Rankin scale (attachment)	+			+	+
Assessment of vital functions (BP, RR, pulse, T)	+			+	
Haematology	+			+	
Serum biochemistry	+			+	
CRP		+			
ECG	+				
Assessment of the presence and severity of adverse events		+	+	+	

Schedule of the clinical study procedures

* For patients, eligible for advanced brain imaging at the tertiary stroke center.

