1. DESCRIPTION OF EFFICACY CRITERIA

1. Development of hemorrhagic transformations

Development of hemorrhagic transformations (HT) in ischemic area should be determined based on the results of follow-up brain CT. According ECASS 3 criteria, HT is defined as symptomatic (SHT) when neurological symptom exacerbation according to NIHSS is \geq 4 NIHSS or results in death.

2. NIHSS scale

Neurological deficit is assessed using NIH scale. It is a 15-item scale evaluating level of consciousness, gaze, visual field, facial palsy, motor functions, limb ataxia, aphasia, dysarthria as well as extinction, and inattention (Brott et al, 1989).

Each item has a 3-5 score from 0 to 4, with the highest score being consistent with the most severe disability. The worst score is assigned in case of death.

Drastic improvement - cases of improvement with reduced NIHSS score ≥ 4 one day after the disease debut is considered as "drastic improvement".

3. Modified Rankin Scale

Modified Rankin Scale (Van Swieten et al, 1988) is the scale evaluating general functional outcome. It is used to grade the stroke outcome and post-stroke disability. Modified Rankin scale is the ordinal 7-point scale scoring from 0 (lack of residual symptoms) to 6 (worst) which corresponds to patient death.

4. Neuroimaging techniques

Brain non-contrast CT will be performed at admission, in 24 h, on day 7 and 14 after IVT using standard technique; helical scanning is preferred; minimum section width (post reconstruction) is 5 mm; scanning area - the whole brain; the sections are made without gantry slope.

The sections obtained at admission will be assessed using ASPECTS scale indicating the presence of the symptom of hyperdense middle cerebral artery (MCA) sign.

Hyperdense MCA sing is determined based on the density of affected and normal vessels. Absolute density of affected MCA > 43 Hounsfield units and affected/normal MCA > 1.2 on non-contrast CT is considered as a positive symptom.

24 hours, on day 7 and 14 after IVT non-contrast CT is performed to evaluate presence of haemorrhagic transformation.

Advance brain imaging protocol:

Non-contrast MRI will be performed at admission. Axial DWI, FLAIR, MR-angiography are performed using standard techniques.

In 24 h after IVT non-contrast brain MRI is carried out in DWI, DTI and MR-angiography.

DWI is used to determine infarction volume using ABC/2 formula.

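### Infarct volume is calculated only after treatment starts, although the admission DWI could supply a same-measure baseline covariate at little cost

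*Protocol*

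**What the plan says.** The synopsis lists amelioration of ischaemic brain injury (neuroprotection) as an additional objective. Under Additional evaluation (advanced brain imaging) it fixes the volume measurements: "The infarct volume was calculated on DWI (at V1) and CT (at V3) scans according to the ABC/2 method".

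On timing, the synopsis (Length of the Study) says: "Cerebrolysin treatment would be initiated simultaneously with IVT and continued once daily for 14 consecutive days". Visits are "screening (on admission), in 24 h (visit 1), on day 7, 14, and 90", so V1 falls about a day after the first infusion and V3 at day 14.

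On the admission scan, Efficacy Evaluation section 1, item 4 (Neuroimaging techniques) says: "Non-contrast MRI will be performed at admission. Axial DWI, FLAIR, MR-angiography are performed using standard techniques". The Schedule of the clinical study procedures places the same MRI in the screening column for patients eligible for advanced imaging at the tertiary centre. Clinical Study Design section 6 puts brain MRI at enrolment, ahead of randomisation and the first dose. The additional inclusion criteria for advanced imaging require "Stroke in the middle cerebral artery territory with a minimum diffusion-weighted imaging (DWI) lesion diameter of 20 mm on admission".

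Item 4 of the efficacy section also says that DWI serves to obtain infarct volume by ABC/2. It names no visit there, but the statement follows directly on the 24 h MRI, which agrees with V1 in the synopsis.

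**The concern.** Infarct volume after treatment depends heavily on how large the lesion was at entry. With no admission volume, that source of variation stays in the error term, and the trial cannot check whether the arms began with similar lesions. Two features make this more noticeable here. Advanced imaging is confined to eligible patients at one tertiary centre. Allocation is by a single unstratified list of Bernoulli draws with probability 0.333, so nothing balances lesion size within the subset.

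The Protocol recognises lesion heterogeneity for the DTI and permeability measures and handles it by reference to the opposite hemisphere. Infarct volume has no comparable device, although the scan that could provide one is acquired anyway.

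**Working it through.** **What exists before treatment**

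| Scan | Timing | ABC/2 volume planned? |
|---|---|---|
| Admission DWI (imaging subset) | before first dose | no; lesion diameter only, for eligibility |
| V1 DWI | about 24 h after first dose | yes |
| V3 CT | day 14 | yes |

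Because eligibility requires a lesion of at least 20 mm on the admission DWI, every patient in the subset should have a lesion visible enough for an ABC/2 reading.

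**Precision.** The Protocol gives no sample size, standard deviation or correlation for infarct volume, so there is no figure of its own to reproduce. Let ρ be the correlation between admission and later (log) volume. Against an unadjusted comparison at one visit, covariate adjustment multiplies the variance of the arm difference by 1 − ρ², equivalent to 1/(1 − ρ²) times the patients. All values of ρ are assumptions.

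| ρ | 1 − ρ² | 1/(1 − ρ²) |
|---|---|---|
| 0.3 | 0.91 | 1.10 |
| 0.5 | 0.75 | 1.33 |
| 0.7 | 0.51 | 1.96 |
| 0.8 | 0.36 | 2.78 |

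**Illustration in power.** Assume a subset of 60 split 20:40, a true difference of 0.5 SD and two-sided α of 0.05. The unadjusted standard error is √(1/20 + 1/40) = 0.27 SD and power is 45%. With adjustment the standard error is multiplied by √(1 − ρ²), and power becomes 48%, 56%, 72% and 86% at ρ = 0.3, 0.5, 0.7 and 0.8.

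**Chance imbalance.** In the same assumed subset, the arm difference in admission volume also has a standard error of 0.27 SD. An imbalance above 0.3 SD in either direction then occurs with probability P(|Z| > 0.3/0.27), about 27%. At ρ = 0.7 an imbalance of 0.3 SD shifts the follow-up difference by 0.7 × 0.3 = 0.21 SD.

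**Against a comparison already adjusted for ASPECTS or NIHSS.** If those scores correlate r₀ with later volume and carry only information that admission volume also carries, the further gain is (1 − r₀²)/(1 − ρ²). At ρ = 0.7 this is 0.91/0.51 = 1.78 for r₀ = 0.3 and 0.75/0.51 = 1.47 for r₀ = 0.5, against 1.96 with no other covariate.

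**Why a covariate and not a change score.** With equal variances, change from admission multiplies the variance by 2(1 − ρ): 1.40 at ρ = 0.3, 1.00 at 0.5 and 0.60 at 0.7. It helps only when ρ exceeds 0.5. Covariate adjustment does not have that drawback.

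**The case against.** The strongest reply is that nothing in the Protocol is wrong. Both arms are measured with the same modality at each visit, so the DWI/CT switch does not enter the arm comparison, and randomisation keeps that comparison unbiased. Its standard error already allows for chance differences at entry. This stands in full.

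A reader might infer that the plan treats the DWI-to-CT difference as infarct growth, or uses V1 volume as a baseline and so adjusts away an effect in the first 24 h. The documents do not support this: they list two measurements and plan neither analysis. Nor does the neuroprotection objective as a whole lack a reference. The DTI and permeability measures are set against the mirrored contralateral region, and ASPECTS and NIHSS are both recorded at admission.

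It can also be said that the choice of covariates belongs in the statistical analysis plan, and that the admission scan can be read later. The first part is fair for the model. The visits at which a quantity is measured, however, are protocol content, and the synopsis names them without admission. The second part means that no data are lost, which keeps the matter small.

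Finally, ρ is unknown. The 20 mm threshold narrows the range of admission lesions, and the link to a day-14 CT volume may be weaker than to a 24 h DWI volume. The low end of the range must therefore be taken seriously, and there the gain is slight.

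**Conclusion.** The point holds as a cheap improvement, not as an error. Infarct volume is planned only after treatment begins, and an available pre-treatment scan is used for eligibility but not for volume. The cost is precision and the lack of a direct check on lesion size at entry. Bias is not at issue.

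The size rests wholly on the assumed ρ. The gain is equivalent to between 1.1 times (ρ = 0.3) and 2.8 times (ρ = 0.8) the imaged patients against an unadjusted comparison, and is smaller to the extent that ASPECTS or NIHSS would already be adjusted for. The power figures further assume a subset of 60 and a difference of 0.5 SD; the Protocol gives neither. Importance is low, because the objective is an additional one and the synopsis declares the whole analysis exploratory.

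**What to change.** In the synopsis (Additional evaluation) and in Efficacy Evaluation section 1, item 4, state that ABC/2 volume is also calculated on the admission DWI, by the radiologists who are already blinded to allocation. Compare log volume between arms at V1 and at V3 separately, each adjusted for log admission volume. If a V1-to-V3 change is reported at all, state that it is not to be read as growth, because the modality differs. Settle this before any comparison by arm, since the synopsis places the detailed statistical analysis plan after study completion.

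The cost is a few minutes of extra reading per imaged patient. No new scan, visit or staff is needed.

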1. STUDY PRODUCT

Cerebrolysin is a solution for injection.

Cerebrolysin is a peptide product derived biotechnologically by standardised fermentative splitting of purified and lipid-free cerebral proteins. It consists of neuropeptides with low molecular weight (< 10 kDa) and free amino acids. Cerebrolysin has been authorised and approved for commercial distribution for the treatment of stroke and dementia in numerous European and Asian countries.

2. BACKGROUND DATA

Generally, cerebrolysin imitates effect of neurotrophic factors and exhibits neuroprotective (Wronski et al 2000), neurotrophic (Akai et al. 1992, Satou et al. 1994), and neuroplastic effects. Pharmacological data obtained in numerous clinical studies in vitro including biochemical experiments and cell culture models definitely revealed these neurotrophic and neuroprotective properties of the product. Cerebrolysin protects cerebral neurons against stroke-induced hypoxic and ischemic damage addressing various states of the ischemic cascade. The product provides positive effect on cerebral metabolism by increasing efficiency of the cascade of aerobic reactions associated with significant lactate level decrease. It neutralises glutamate-induced excitotoxicity by binding with the receptors of inhibitory neurotransmitters resulting in increased neuronal viability. In addition, cerebrolysin was found to prevent cell death by suppressing production of free acid radicals and affecting expression of antioxidant enzyme genes. Cytoskeletal proteins such as MAP2 resulting from ischemic damage tend to be stabilised by cerebrolvsin accounting for preservation of the structural cell integrity and, probably, bloodbrain barrier (BBB). Most importantly, hypoxia model on animals confirmed penetration of cerebrolysin neuropeptides through BBB into cerebral parenchyma after intravenous administration unlike natural neurotrophic factors. Hypoxia and ischemia models in animals also revealed cerebrolysin potential to prevent cytoskeletal degeneration, reduce swelling and decrease lethality. Furthermore, the model of acute focal ischemia in rats demonstrated that administration of cerebrolysin within 2 hours post ischemic episode was able to reduce infarction area and improve neurological outcome (Hanson, 2009).

Cerebrolysin was found to be effective as neuroprotective support to thrombolytic therapy in terms of stroke outcomes, especially at long-term administration of the product against step-wise neurorehabilitation (Wolf-Dieter Heiss et al., 2012). The peculiarities of multimodal effect of cerebrolysin demonstrated on the experimental models suggested a hypothesis of efficacy of this product during intravenous thrombolytic therapy. The clinical study carried out by W. Lang et al. 2012 evidence that the patients receiving cerebrolysin as add-on to thrombolytic therapy had significantly faster treatment response compared to those receiving thrombolytic therapy only.

This clinical study is designed to evaluate efficacy of drug protection of cerebral tissue, predominantly against reperfusion damage during reperfusion therapy.

3. POTENTIAL RISKS AND BENEFITS FOR HUMAN

Currently, the results of 60 controlled clinical studies of cerebrolysin have been published. In these clinical studies, 2,905 patients received cerebrolysin; these patients reported 835 adverse events (28.74 event per 100 patients). For comparison, 2,594 placebo-treated patients reported 629 adverse events (24.25 events per 100 patients). These results suggest that in cerebrolysin group average adverse event rate of 12.1 % was slightly higher compared to placebo group (9.6 %). Summarising, we may conclude that the safety data from both controlled and uncontrolled clinical studies of cerebrolysin demonstrate excellent benefit/risk ratio.

4. DESCRIPTION OF THERAPY

Study product cerebrolysin is expected to be administered at a daily dose of 30 mL diluted in 0.9 % sodium chloride up to 100 mL as a 20-minute intravenous infusion. The infusion of the study product will be initiated simultaneously with bolus administration of rt-PA, the products will be injected using different access routes (e.g. using a cubital catheter of right and left cubital veins). Where indicated baseline therapy (e.g. BP-controlling products) will be administered prior to or after the first infusion of the study product and thrombolytic infusion. Subsequent infusions of cerebrolysin will be made on a daily basis at the same time for 14 days.

5. CLINICAL STUDY COMPLIANCE

The clinical study will be carried out in accordance with this protocol, ICH GCP and current requirements of the national regulatory authorities. The study was approved by the Local Ethics Committee of the Interregional Clinical Diagnostic Center, Kazan, Russia (Protocol #81 of 04/24/2018). All recruited subjects or their legal representatives would sign written informed consent. The study methods would be performed in accordance with the Declarations of Helsinki.

6. REFERENCE INFORMATION

Stroke is a severe disease and one of the leading causes of disability and lethality globally. Ischemic stroke (IS) accounts for the most part of stroke cases overall, i.e. up to 85 %. Reperfusion therapy is currently one of the verified effective IS treatment. IV TLT is deemed to be effective in improving neurological symptoms while reducing NIHSS by ≥ 4 within one day. One of the factors of reperfusion therapy failure may be reperfusion damage developing after recanalisation of a cerebral vessel and generally is considered as a consequence and progression of abnormal ischemic effects. Therefore, recanalisation of a clotted or embolised cerebral vessel within "therapeutic window" promotes preservation of the most part of inactive though viable neurons; meanwhile recovery of blood flow in ischemic area may cause reperfusion-induced cerebral tissue damage of various grades, thus aggravating peracute IS.

One of manifestations of reperfusion damage is BBB failure with increased permeability or impaired integrity resulting in exacerbation of edema of ischemic area or in hemorrhagic transformation (HT) of the ischemic area. Meanwhile, HTs are also reported without recanalisation effect and outside of the ischemia area; this is due to both cerebral tissue damage in hypoperfusion area and due to toxic effect of the thrombolytic agent. Thus, TLT increases the risk of HT 4-10-fold by activating matrix metalloproteinase 9, 2, 3 in neutrophils, endothelium, astrocytes, and platelet-derived growth factor-CC, however the pathogenesis of early (up to 24 hours) HTs and late HTs varies. While early HTs are associated with acute processes of BBB damage, the late ones are due to cerebral tissue inflammation and vascular remodelling. Clinically, the most relevant are symptomatic HTs (SHT) associated with aggravated neurological symptoms \geq 4 according to NIHSS scale or lethality (according to ECASS III 2008, 2016). Generally, SHTs have the nature of parenchymatous haematomas (hemorrhages, PH2 according to neuroimaging HT classification) exceeding 30 % at ischemic area. Smaller haematomas and petechia-like HTs are asymptomatic (HI-1, HI-2, PH-1).

Development of the principles of pharmacological protection of cerebral tissue against reperfusion damage, one of the modifiable factors defining severity of cerebral damage and, therefore, neurological deficit and rehabilitation potential, is a promising trend in the treatment of acute cerebral ischemia.

Cerebrolysin has been approved for the treatment of stroke in more than 45 countries globally.

Significant progress has been made in stroke therapy since approval of cerebrolysin, including improved general care and condition of stroke units, rehabilitation became more targeted, fibrinolytic therapy (rt-PA, Actilise) - more commonly available in global specialised centers.

CLINICAL STUDY PURPOSES AND OBJECTIVES

The purpose of this study is to investigate the effect of cerebrolysin on post-reperfusion period in patients with ischemic stroke during thrombolytic therapy with decreased frequency of HTs. In addition, it is planned to study the hypothesis that cerebrolysin group will show better ischemic area and BBB changes, better general neurological status and functional outcomes.

CLINICAL STUDY DESIGN

